## 5. Methodology Plan

We will conduct an observational study to compare 1) the proportion of COVID-related participant factors (including financial hardship and distress among WOC who decline participation in TMIST (EAQ201 participants) compared to non-WOC EAQ201 participants; and 2) effects of federal-, state- and local-level COVID-19 factors on TMIST participation, in WOC vs non-WOC. The primary objective compares COVID-related financial hardship between WOC vs non-WOC EAQ201 participants (see **Table 1** definition). Federal-, state-, local-, practice- and participant-level moderators (see Fig. 1 conceptual model) will be evaluated with hierarchical regression models. For the exploratory objectives, we will compare the effects of federal-, state- and local-level COVID-related factors on TMIST participation (secondary outcome), stratified by WOC vs non-WOC. Any woman 45-74 years old who is scheduled for breast cancer screening and is eligible for TMIST but declines will be approached by the TMIST site research associates (RAs). Enrollment for TMIST typically occurs immediately prior to the scheduled breast screening visit. Solicitation for participation in EAQ201 will occur at the same time for those who decline TMIST. TMIST site RAs will ask women who decline TMIST if they are interested in participating in EAQ201.

Sites participating in the parent study may approach potential participants using written materials, by phone or at the time of screening mammography. We will use the same enrollment processes. For those who are approached by phone and who decline to participate in TMIST will be recruited for EAQ201 during the same call.

For those sites that use the written materials, it is up to the participant to actively respond to the site at which point they are additionally screened for eligibility for TMIST, usually by phone. Among those who respond to written materials and are additionally screened by phone, we will be able to approach the women who decline to participate in TMIST for EAQ201 recruitment.

Paper documentation of consent is required. It may be signed when the participant attends the scheduled screening mammogram.

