EAQ201 project manager will create a list of eligible sites based on EA1151 recruitment and enrollment status and will notify CTSU of ECOG-ACRIN clearance of this site qualification criteria. Site submission of required IRB documentation to NCI CIRB will be monitored in RSS weekly by the EAQ201 project manager who will report site activation clearances in CTSU weekly to the EAQ201 study chair by [define weekly communication mechanism you prefer here]. All sites that plan to open EAQ201 are strongly encouraged to activate EAQ201 within 30 days of ECOG-ACRIN activation of the trial as there will be no maximum number of subjects that can be enrolled in the trial at any one site and enrollment is expected to be completed within a few months.

EAQ201 project manager will reach out weekly to all eligible EA1151 sites to remind them about the EAQ201 study and obtain IRB approval through NCI CIRB. This outreach will occur by email to TMIST PI and TMIST lead coordinator until the site opens EAQ201, declines to participate, or EAQ201 enrollment reaches 50% of planned enrollment, 500.

**Participant Recruitment Plan:** All participating EAQ201 TMIST sites will be expected to approach at least 20 women per month in person or over the phone as part of their TMIST recruitment effort while EAQ201 is open to participant enrollment with at least 5 women approached that are classified as Women of Color [definition] according to information documented in the site's electronic medical record system.

All women presenting for screening mammography who meet the eligibility criteria for EA1151 but ultimately decline to participate in EA1151 should be immediately invited to participate in EAQ201 by EA1151 site designated recruiters.

All EAQ201 TMIST sites are expected to keep local TMIST recruitment logs for duration of EAQ201 enrollment period. The first two weeks of local TMIST recruitment logs for each site are to be submitted to the EAQ201 project manager to confirm that recruitment effort is happening for TMIST and to monitor number of WOC TMIST declines at the site. This information will be summarized across all sites for reporting to the EAQ201 central trial team to compare to EAQ201 enrollment rates at each site to determine if site is on track to complete within timeline planned and that overall WOC versus non-WOC participation ratio is within 10%-25% range planned.

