7.2 Primary Objective

The primary objective is to compare the proportion of WOC EAQ201 participants who experience COVID-related financial hardship vs non-WOC EAQ201 participants. The results, with and without adjustment for missing values (see [7.5](#)), will be compared as a sensitivity analysis. Logistic regression models, with and without stratification by WOC status, will be fit with financial hardship as the response variable to investigate other sociodemographics (e.g., age, marital status, insurance status) and state- and local-level factors (e.g., state COVID severity, shelter-in-place policies, state and local unemployment during shelter-in-place) as moderators.

Sample Size Considerations for the Primary Objective ([7.1.1](#)):

The primary objective is to compare the proportion of WOC EAQ201 participants who experience COVID-related financial hardship (see **Table 1** for definition) with the proportion of non-WOC EAQ201 participants who experience COVID-related financial hardship. The National Bureau of Economic Research estimated unemployment rates by race and ethnicity in April 2020, around shelter-in-place regulations. Unemployment in African-American and Latinx populations averaged 18% compared to Whites (13%). At a sample size of 1000 women who decline TMIST participation, we expect to recruit at least 10-25% WOC into this study. Assuming alpha of 0.05, we estimated power over a range of differences across various proportions (see **Table 4**). For instance, at a sample size of 1000 with 10% of WOC, we have 77% power to detect a minimum difference of 0.10 between two proportions (0.2 vs. 0.1); at a sample size of 1000 with 25% of WOC, we have 88% power to detect a minimum difference of 0.08 between two proportions (0.18 vs. 0.1). Please note that based on DCP-001, 16% of the women who declined TMIST were WOC. Accrual onto TMIST is expected to continue for another 4.4 years. Also based on DCP-001 and extrapolating to the Non-NCORP US sites, accruing 1,000 women to this study is achievable. We do not envision any danger that this study will close due to lack of accrual.

**Table 4: Estimated power for a two-sample proportions using Fisher's Exact test (two-sided). N1: # of WOC; N2: # of non-WOC**

Sample size (N)	N1/N2	P1 (WOC)	P2 (non-WOC)	Delta	Alpha	Power
(Sample size: 1000; N1/N2=1/9, i.e.,10% of WOC)						
1000	1/9	0.200	0.100	0.100	0.05	0.77
1000	1/9	0.225	0.100	0.125	0.05	0.90
1000	1/9	0.250	0.100	0.150	0.05	0.96

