### 7.3 Secondary Objectives

Two-sample proportion tests (e.g., Z-test based on normal approximations or Fisher's exact test) will be used to compare the proportions of WOC vs non-WOC EAQ201 participants with 1) COVID-related change in their material condition; 2) COVID-specific perceived financial distress. Logistic regressions may be performed to adjust for potential confounders during the comparisons. Missing data will be managed as below (See [7.5](#)).

The proportion of WOC in EAQ201 participants will be compared to the proportion of WOC in TMIST participants using the one-sample proportion test. Based on the TMIST data, the proportion of WOC in TMIST participants is around 25%. Then we will have 80% power to detect a difference of 3.9% using a two-sided exact test with a significant level of 0.05.

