### 7.4 Assess the effects of sociodemographic characteristics, and federal-, state- or local-level COVID-19 factors on TMIST participation, in WOC vs non-WOC.

For the exploratory objective ([7.1.3.5](#)), we will compare the effects of sociodemographic characteristics, federal-, state- or local-level factors (e.g. maximum number of COVID-19 cases, state unemployment during shelter-in-place, local unemployment during shelter-in-place) on TMIST participation, stratified by WOC vs non-WOC. We will fit a logistic regression model with TMIST participation status (EAQ201 participant or TMIST participant) as the response variable to investigate other sociodemographic (e.g., marital status, neighborhood SES, insurance type), federal-, state- or local-level factors (see **Table 2**). Regression modeling will be conducted with and without stratification by WOC vs non-WOC.

The analysis set will include the 1000 EAQ201 participants from this study and a corresponding number of TMIST participants, who will be randomly selected from the enrolled participants in the main TMIST study. The selection will be stratified by site and enrollment time. Assuming that the proportion of overall EAQ201 participants is from 0.20 to 0.50, **Table 5** below shows the power analysis of testing for the odds ratio in the logistic regression. The variables of interest can be continuous or categorical (binary). For instance, 2000 women (1000 EAQ201 participants versus 1000 randomly selected TMIST participants) achieves 90% power at a 0.050 significance level to detect a change in the proportion of EAQ201 participants from 0.50 at the mean of the testing variable to 0.538 when the value of the variable is increased to one standard deviation above the mean. This change corresponds to an odds ratio of 1.165. An adjustment was made since a multiple regression of the independent variable of interest on other independent variables in the logistic regression obtained an R-Squared of 0.10.

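### Section 7.4 stratifies TMIST selection by site and time but does not carry this into the model: state-level effects may be matched out, and Table 5's 90% power does not cover them

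*Combined protocol and SAP*

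**What the plan says.** Section 7.4 serves exploratory objective 7.1.3.5. Its analysis set is the 1,000 EAQ201 women plus "a corresponding number of TMIST participants, who will be randomly selected from the enrolled participants in the main TMIST study". It adds: "The selection will be stratified by site and enrollment time". Only overall ratios appear: 1:1 in the worked example, and for Table 5 "Assuming that the proportion of overall EAQ201 participants is from 0.20 to 0.50". Nothing says how many TMIST women come from each site-by-time stratum.

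The model is a logistic regression of EAQ201 versus TMIST status, used to "investigate other sociodemographic (e.g., marital status, neighborhood SES, insurance type), federal-, state- or local-level factors", with and without stratification by WOC status. No site or time term, conditional likelihood, clustering, weight or offset is named. Table 5 then gives 90% power at an odds ratio of 1.165 per standard deviation (SD) for variables of interest in general, with no exception for state-level ones.

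Section 5 defines the state-level COVID variables with one value per state, such as the maximum one-day count. It also says that multilevel "moderators (see Fig. 1 conceptual model) will be evaluated with hierarchical regression models". That sentence follows the primary objective, and Section 7.4 does not repeat it.

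**The concern.** A factor with one value per state is constant within a site. Whether its effect can be seen depends entirely on how the EAQ201-to-TMIST ratio is allowed to vary between sites, and the selection rule sets that ratio. One reading of the rule fixes it by design. The other leaves it to depend on how readily decliners at each site join EAQ201, a second selection step that the section does not mention.

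The analysis could therefore report no state-level effect because the design removed it, or report one produced by uneven uptake. Either result would be credited with 90% power at 1.165. The objective names these factors as targets, and Section 1.2 attaches a hypothesis to them.

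**Working it through.** **1. Table 5, first row.** Inputs from Section 7.4: 90% power, alpha 0.05, P0 = 0.50, odds ratio 1.165 per SD, R-squared 0.10. With a two-sided Wald test,

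N = (1.960 + 1.2816)² / [P0(1 − P0) × (ln 1.165)² × (1 − R²)] = 10.507 / (0.25 × 0.02332 × 0.90) = 2,002,

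against 2,000 stated. A one-sided test would need 1,632. All twelve rows of Table 5 reproduce to within 3% of N. The formula treats women as independent and contains no term for sites or selection.

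**2. What the model estimates.** At site s, let d be the fraction of approached women who decline TMIST, u the fraction of decliners who join EAQ201, and f the fraction of TMIST enrollees selected. In the analysis set,

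log odds of EAQ201 status = logit(d) + ln(u) − ln(f).

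The effect wanted is the slope of logit(d) on the state factor.

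**3. Strata filled to EAQ201 counts.** Here f is chosen so that the log odds is 0 in every stratum. The slope is 0 and the odds ratio is 1, whatever d does. Any constant ratio per stratum gives the same result.

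- Simulation (50 sites assumed), true odds ratio 1.165: fitted 1.000, 0% rejection.
- Random site intercept, true odds ratio 1.5: fitted 1.000, 0% rejection.
- Site fixed effects: the design matrix has rank 50 with or without the state factor.
- Adjusted model: suppose a person-level covariate has log odds ratio 0.4 and its mean shifts by 0.3 per SD of the state factor. Keeping the stratum log odds at 0 forces a coefficient of about −0.3 × 0.4 = −0.12 on the factor, or exp(−0.12) = 0.89. The opposite shift gives exp(0.12) = 1.13. Simulated with true odds ratio 1.165: 0.90 (87% rejection) and 1.13 (93%). With true odds ratio 1.0 and the positive shift: 0.89 (90%). A weaker covariate (shift 0.15, log odds ratio 0.2) gives 0.97 and 0% rejection.
- Preserved with site effects: a person-level odds ratio of 1.165 (fitted 1.17, 92% rejection) and a WOC-by-factor interaction of 1.25 (fitted 1.26).
- Separate WOC-stratum odds ratios are distorted. True 1.2 (non-WOC) and 1.5 (WOC) come out as 0.96 and 1.18, although their ratio survives (1.25 true, 1.18/0.96 = 1.23 fitted).
- ZIP-level factors are only attenuated in the plain model: a true 1.165 gives 1.04 or 1.08 with 25% or 50% of the variance within site.

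**4. Selection proportional to TMIST enrollment.** Now f is constant, so the fitted odds ratio is about the true odds ratio times the uptake ratio per SD of the factor (50 sites in 20 states, 600 runs).

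| True OR | Uptake ratio per SD | Product | Simulated OR |
|---|---|---|---|
| 1.165 | 1.000 | 1.165 | 1.166 |
| 1.165 | 1.165 | 1.357 | 1.36 |
| 1.165 | 0.858 | 1.000 | 1.00 |
| 1.000 | 1.165 | 1.165 | 1.17 (96% false rejection) |

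Uptake that is uneven but unrelated to the factor (log-SD 0.5) leaves the estimate at 1.16 to 1.17. It damages the standard error instead. For the plain model with proportional stratified selection:

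| Assumed between-site variation | False positives | Rejection at OR 1.165 |
|---|---|---|
| None | 1% or less | 97% to 97.5% |
| Log-uptake SD 0.25 | 11% | – |
| Log-uptake SD 0.5 | 38% | – |
| Decline rate, logit SD 0.3, equal uptake | 11% to 14% | 81% to 86% |

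Ranges are across simulations with 20 or 25 states.

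**5. Power with valid inference.** The design effect is 1 + (m − 1) × ICC. With 40 clusters of 50 women and ICC 0.02 it is 1 + 49 × 0.02 = 1.98, the effective N is 2,000/1.98 = 1,010, and power at 1.165 is 63%. Over 20 to 100 clusters and ICC 0.01 to 0.05, power runs from 26% to 84%.

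**6. Repairing a count-matched sample.** With −ln(TMIST sampling fraction) as an offset, a true 1.165 is fitted as 1.15 to 1.16, again if uptake is unrelated to the factor. Site-clustered standard errors still gave 8% to 13% false positives with 50 sites.

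**The case against.** The strongest reply has four parts.

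- **It is exploratory.** True, and this limits the consequence. But the objective has its own section and power table.
- **Section 5 promises hierarchical models.** The same paragraph names effects on TMIST participation as the second aim, so they may be meant for Section 7.4. If so, the plain-model false-positive rates above would not describe the plan. A random site effect still cannot restore a matched-out effect or correct uptake that tracks the factor.
- **Uneven uptake is not shown.** Section 5 says "there will be no maximum number of subjects that can be enrolled in the trial at any one site", which concerns counts, not the fraction of decliners who join. Sites are told to invite every decliner immediately and to keep recruitment logs throughout, so uptake could partly be measured. This stands: the documents show that nothing secures the assumption, not that it fails.
- **Table 5 is generic.** It never claims 90% for state-level factors by name, but it excludes none, and the section's leading examples are state-level.

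A reader might infer more than the documents support. Table 5 is not miscalculated. State-level effects are not lost under every reading, since proportional selection keeps them. Unequal uptake does not by itself bias the estimate; correlation with the factor does. Nor would equal uptake rescue Table 5, because variation in decline rates alone inflates the error rate. The Section 1.2 hypothesis of a stronger effect in WOC is not untestable: the interaction is identified within strata.

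**Conclusion.** The point holds for exploratory objective 7.1.3.5 only and should be fixed. Under count-matching, an unadjusted odds ratio of 1 follows from algebra and needs only that the factor be constant within site. If state is assigned from a woman's own ZIP, sites near a state border would leave a little within-site variation. Under proportional selection, the 11% to 38% false-positive range and the power loss rest on assumed numbers of sites and states, ICC, and variation in uptake and decline rates, because the documents give none. The direction of the error is firm; its size is illustrative. The 90% power figure is sound for person-level covariates and unsupported for state-level ones.

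**What to change.** 1. State the allocation rule in Section 7.4. If state-level main effects are wanted, do not fill strata to EAQ201 counts: select in proportion to TMIST enrollment, or use the known sampling fractions as an offset or weight. If count-matching is kept, analyse conditionally on site and time, and limit claims to person-level factors, within-site factors and the WOC-by-factor interaction.
2. Use random-site or site-clustered inference for state- and local-level factors, with a small-sample correction if clustered, and state that Section 5's hierarchical models apply here.
3. State the assumption that EAQ201 uptake among decliners is unrelated to the factor, and check it against the site recruitment logs described in Section 5.
4. Restrict Table 5's 90% power to person-level covariates.
5. Minor: remove marital status from the model examples or reconcile it. Section 5 limits the comparison to data collected in both studies, and Table 1 does not list marital status for TMIST participants.

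The cost is SAP wording plus stratum totals from TMIST enrollment counts. Only the first two weeks of logs are submitted centrally, so a fuller uptake check would need the rest from the sites. The price is narrower state-level claims and a less favourable power statement.

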**Table 5: Tests for the Odds Ratio in Logistic Regression (Wald Test)**

**A. X is continuous**

Power	N(EAQ201 participants)	N(TMIST participants)		P0	P1	Odds Ratio	R-SQRD	Alpha	Beta
	(50% EAQ201 participants)								

0.9	1000	1000		0.5	0.538	1.165	0.1	0.05	0.1
0.9	1500	1500		0.5	0.531	1.133	0.1	0.05	0.1
(40% EAQ201 participants)									
0.9	1400	2100		0.4	0.429	1.125	0.1	0.05	0.1
0.9	2100	3150		0.4	0.423	1.101	0.1	0.05	0.1
(20% EAQ201 participants)									
0.9	1200	4800		0.2	0.218	1.117	0.1	0.05	0.1
0.9	1800	7200		0.2	0.215	1.094	0.1	0.05	0.1
B. X is categorical (binary)									
Power	N		% N X=1	P0	P1	Odds Ratio	R- SQRD	Alpha	Beta
(50% EAQ201 participants)									
0.9	1000	1000	50	0.5	0.576	1.359	0.1	0.05	0.1
0.9	1500	1500	50	0.5	0.562	1.284	0.1	0.05	0.1
(40% EAQ201 participants)									
0.9	1400	2100	50	0.4	0.457	1.263	0.1	0.05	0.1
0.9	2100	3150	50	0.4	0.447	1.21	0.1	0.05	0.1
(20% EAQ201 participants)									
0.9	1200	4800	50	0.2	0.236	1.239	0.1	0.05	0.1
0.9	1800	7200	50	0.2	0.23	1.192	0.1	0.05	0.1

## 7.5 Handling Missing Data

As stated above, we will closely monitor the participant attrition and determine whether the dropout is informative or not. If the missing is random, we may implement a method like multiple imputation to impute the missing values. In case the missing is not random (e.g., participants who are lost to follow up may experience more financial burden), we will implement various methods for the adjustment in our analysis, e.g., Bayesian modeling with informative priors. Analysis under different scenarios will be conducted to explore sensitivity to different missing data assumptions.

## 7.6 Gender and Ethnicity

Based on TMIST data from participants enrolled in September 2020, at sites in the United States, the anticipated accrual in subgroups defined by gender and race is:

Racial Categories	Not Hispanic or Latino Female	Not Hispanic or Latino Male	Hispanic or Latino Female	Hispanic or Latino Male	Total
American Indian/ Alaska Native	2	0	0	0	2
Asian	19	0	0	0	19
Native Hawaiian or Other Pacific Islander	1	0	0	0	1

Racial Categories	Not Hispanic or Latino Female	Not Hispanic or Latino Male	Hispanic or Latino Female	Hispanic or Latino Male	Total
Black or African American	196	0	2	0	198
White	742	0	30	0	772
More Than One Race	6	0	2	0	8
Total	966	0	34	0	1,000

## 7.7 Study Monitoring

This study will be monitored by the Data Safety Monitoring Committee (DSMC). The DSMC will meet twice each year. For each meeting, the study is reviewed for safety and progress toward completion. These group meeting reports are made available to the local investigators, who may provide them to their IRBs. Prior to completion of this study, any use of outcome data will require approval of the DSMC. Any DSMC recommendations for changes to this study will be circulated to the local investigators in the form of addenda to this protocol document.

This protocol will be monitored under the jurisdiction of the EA1151 (TMIST) DSMC.

The Brown office of the Statistics Center has extensive and long-term experience in monitoring large screening trials, including ACRIN 6652 (Digital Mammography Imaging Screening Trial), ACRIN 6654 (National Lung Screening Trial), ACRIN 6664 (National CT Colonography Trial), and ACRIN 6666 (Screening Breast Ultrasound in High-Risk Women). Established approaches and practices for study monitoring in our organization will be followed and adapted to meet the monitoring needs of this protocol.

We will learn from the experiences of the ongoing SWOG 1417CD trial investigating financial burden in metastatic disease.

In addition to site visits and available phone and email support, as outlined above, the EASEE-PRO system will send email notifications and up to 3 follow-up reminders to notify web-based participants to complete surveys. If a participant is non-compliant, the OEAU may contact the site CRA and/or the participant in an effort re-establish contact, remove barriers, and obtain the survey responses. The efforts may include email, mail, and phone contact with no more than 3 attempts by any method (i.e., three failed recovery attempts, at least 3 days apart, will be considered participant refusal.)

